#### **7.5.3. PR and QRS Intervals**

The PR interval (measured in msec) is a measure of the time between the start of the P wave (the onset of atrial depolarization) and the beginning of the QRS complex (the onset of ventricular depolarization). The QRS interval measures the duration of the QRS complex.

VR, PR, RR, and QRS values at each visit and change from baseline at each visit will be summarized for the Safety Analysis Set by treatment group using descriptive statistics.

#### **7.6. Other Safety Measures**

A data listing will be provided for subjects who become pregnant during the study.

#### **7.7. Changes From Protocol-Specified Safety Analyses**

There are no deviations from the protocol-specified safety analyses.

## 8. PHARMACOKINETIC ANALYSES

Plasma concentrations of GS-9876 and filgotinib and the active metabolite of filgotinib, GS-829845, will be listed and summarized using descriptive statistics (eg, sample size, arithmetic mean, geometric mean, % coefficient of variation, standard deviation, median, minimum and maximum).

### 8.1. PK Analyses Related to Intensive PK Sampling

Steady-state PK over a 24 hour dosing interval will be determined in subjects in the PK Substudy Analysis Set. Concentrations of GS-9876, filgotinib, and GS-829845 in plasma will be determined using validated bioanalytical assays.

#### 8.1.1. Estimation of Pharmacokinetic Parameters

PK parameters will be estimated using Phoenix WinNonlin® software using standard noncompartmental methods. The linear/log trapezoidal rule will be used in conjunction with the appropriate noncompartmental model, with input values for dose level, dosing time, plasma concentration, and corresponding real-time values, based on drug dosing times whenever possible.

All predose sample times before time-zero will be converted to 0.

For area under the curve (AUC), samples BLQ of the bioanalytical assays occurring prior to the achievement of the first quantifiable concentration will be assigned a concentration value of 0 to prevent overestimation of the initial AUC. Samples that are BLQ at all other time points will be treated as missing data in WinNonlin. The nominal time point for a key event or dosing interval ( $\tau$ ) may be used to permit direct calculation of AUC over specific time intervals. The appropriateness of this approach will be assessed by the PK scientist on a profile-by-profile basis.

Pharmacokinetic parameters such as  $AUC_{\text{tau}}$ ,  $\lambda_z$  and  $t_{1/2}$  are dependent on an accurate estimation of the terminal elimination phase of drug. The appropriateness of calculating these parameters will be evaluated upon inspection of PK data on a profile-by-profile basis by the PK scientist.

#### 8.1.2. Pharmacokinetic Parameters

PK parameters will be generated for all subjects in the PK Substudy analysis set. The analytes presented in [Table 8-1](#) will be evaluated if data are available.

**Table 8-1. Study Treatments and Associated Analytes**

Treatment	Analyte
GS-9876 10 mg	GS-9876
GS-9876 30 mg	GS-9876
Filgotinib 200 mg	Filgotinib, GS-829845

The analytes and parameters presented in [Table 8-2](#) will be used to evaluate the PK objectives of the study. The PK parameters to be estimated in this study are listed and defined in the Pharmacokinetic Abbreviations section.

**Table 8-2. Pharmacokinetic Parameters for Each Analyte**

Analyte	Parameters
GS-9876	AUC tau , C tau , C max , T max , C last , T last , λ z , CL ss /F, V z /F, and t 1/2 , if appropriate
Filgotinib	AUC tau , C tau , C max , T max , C last , T last , λ z , CL ss /F, V z /F, and t 1/2 , if appropriate
GS-829845	AUC tau , C tau , C max , T max , C last , T last , λ z , and t 1/2 , if appropriate

### **8.1.3. Statistical Analysis Methods**

Individual subject concentration data and individual subject PK parameters for GS-9876, filgotinib, and GS-829845 will be listed and summarized using descriptive statistics by treatment. Summary statistics (number [n], mean, SD, coefficient of variation [%CV], median, min, max, Q1, and Q3) will be presented for both individual subject concentration data by time point and individual subject PK parameters by treatment. Moreover, the geometric mean, 95% CI, and the mean and SD of the natural log-transformed values will be presented for individual subject PK parameter data.

Individual concentration data listings and summaries will include all subjects with concentration data. The sample size for each time point will be based on the number of subjects with nonmissing concentration data at that time point. The number of subjects with concentration BLQ will be presented for each time point. For summary statistics, BLQ values will be treated as 0 at predose and one-half of the lower limits of quantitation (LLOQ) for postdose time points.

Individual PK parameter data listings and summaries will include all subjects for whom PK parameter(s) can be derived. The sample size for each PK parameter will be based on the number of subjects with nonmissing data for that PK parameter.

The following tables may be provided for each analyte by treatment:

- Individual subject concentration data and summary statistics
- Individual subject plasma PK parameters and summary statistics.

The following figures may be provided for each analyte by treatment:

- Individual subject concentration data versus time (on linear and semilogarithmic scales)
- Mean (± SD) concentration data versus time (on linear and semilogarithmic scales)
- Median (Q1, Q3) concentration data versus time (on linear and semilogarithmic scales)

Individual, mean, and median postdose concentration values that are  $\leq$  LLOQ will not be displayed in the figures and remaining points connected.

The following listings will be provided:

- PK sampling details (and PK concentrations) by subject, including procedures, differences in scheduled and actual draw times, and sample age
- Individual data on determination of plasma half-life and corresponding regression correlation coefficient.

## **9. BIOMARKER ANALYSIS**

A separate biomarker analysis plan will document methods to analyze biomarker assessments.

## **11. SOFTWARE**

SAS® Software Version 9.4. SAS Institute Inc., Cary, NC, USA.

nQuery + n Terim Version 4.0. Statistical Solutions, Cork, Ireland.

## 12. SAP REVISION

Revision Date (DD MMM YYYY)	Section	Summary of Revision	Reason for Revision

## 13. APPENDIX

### Appendix 1. Health Assessment Questionnaire Disability Index (HAQ-DI)

The HAQ-DI score is defined as the average of the scores of eight functional categories (dressing and grooming, arising, eating, walking, hygiene, reach, grip, and other activities), usually administered by the patient. Responses in each functional category are collected as 0 (without any difficulty) to 3 (unable to do a task in that area), with or without aids or devices.

The highest score for questions in each category (range 0 to 3) determines the score for the category, unless aids or devices are required. Dependence on equipment or physical assistance increases a lower score (ie, scores of 0 or 1) to the level of 2 to more accurately represent underlying disability. The eight category scores are averaged into an overall HAQ-DI score on a scale from 0 (no disability) to 3 (completely disabled) when 6 or more categories are non-missing. If more than 2 categories are missing, the HAQ-DI score is set to missing. The HAQ-DI can be treated as a continuous measure.

The HAQ-DI score using aids (and/or devices) is computed by taking the maximum score of the questions in each category (range: [0, 3]) and whether or not aids/devices are used (0 or 1):

$$A = \max(\text{dressing \& grooming category questions}, 2*\text{aids indicator}) + \\ \max(\text{rising category questions}, 2*\text{aids indicator}) + \\ \max(\text{eating category questions}, 2*\text{aids indicator}) + \\ \max(\text{walking category questions}, 2*\text{aids indicator}) + \\ \max(\text{hygiene category questions}, 2*\text{aids indicator}) + \\ \max(\text{reach category questions}, 2*\text{aids indicator}) + \\ \max(\text{grip category questions}, 2*\text{aids indicator}) + \\ \max(\text{usual activities category questions}, 2*\text{aids indicator})$$

$$\text{HAQ-DI} = A / (\text{total number of categories with at least 6 non-missing})$$

The following table shows the contribution of the 43 questions used to calculate the HAQ-DI:

HAQ-DI Category:	Category questions: At least 6 categories must have scores to compute the HAQ-DI.		HAQ-DI Category Score with Aids/Devices Calculation:
	Category Questions	Aids/Devices Indicators	
Dressing / Grooming	HAQ0101, HAQ0102 (DRESS, HAIR)	HAQ0114, HAQ0119 (DRSG, GROOM)	Using each question with a scale of 0-3, calculate the category score as the maximum of the category questions.
Arising	HAQ0103, HAQ0104 (STAND, BED)	HAQ0116, HAQ0120 (CHAIR, ARISING)	If the Aids/Devices indicator is "No", no need to adjust the category score.
Eating	HAQ0105, HAQ0106, HAQ0107 (MEAT, LIFT, MILK)	HAQ0115, HAQ0121 (UTENSIL, EAT)	If the Aids/Devices indicator is "Yes" and the category score is <2, then the category score with the Aids/Devices is set to 2.
Walking	HAQ0108, HAQ0109 (WALK, STEPS)	HAQ0110, HAQ0111, HAQ0112, HAQ0113, HAQ0122 (CANE, WALKER, CRUTCH, WHEEL, WALKING)	If the Aids/Devices indicator is "Yes" and the category score is ≥2, then the category score with Aids/Devices is the calculated category score without adjustment.
Hygiene	HAQ0123, HAQ0124, HAQ0125 (WASH, BATH, TOILET)	HAQ0134, HAQ0135, HAQ0137, HAQ0139, HAQ0142 (RAISEAT, BATHBAR, BATHSEAT, LONGBATH, HYGIENE)	For example: The Dressing/Grooming category score is 2 if subject answered 1 for both questions 1 and 2 and "Yes" for both question 14 and 18.
Reach	HAQ0126, HAQ0127 (REACH, BEND)	HAQ0138, HAQ0143 (LONGRCH, REACH)	In the HAQ-DI score calculation, questions on other device/aids will not be used.
Grip	HAQ0128, HAQ0129, HAQ0130 (OPENCAR, JAR, FAUCET)	HAQ0136, HAQ0144 (JAROPEN, GRIP)	
Activity	HAQ0131, HAQ0132, HAQ0133 (SHOP, INCAR, CHORES)	HAQ0145 (ERRAND)	

**Handling Missing Data:** If no more than 2 categories have missing category scores, then the HAQ-DI is the mean of the non-missing category scores. Otherwise, the HAQ-DI score is set to missing.

If any of the category questions are missing, but the aids/device indicator is non-missing, the category score can still be computed. However, if all category questions and its aids/device indicators are missing, then the category score is considered missing.

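### Appendix 1 scores a HAQ-DI category with no functional answer and aids No as 0 (no disability), while its own scoring table gives that category no score

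*SAP*

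**What the plan says.** SAP Appendix 1 describes the HAQ-DI category score in three places.

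- **Formula.** Each category contributes the larger of its question scores and twice the aids indicator. The indicator records "whether or not aids/devices are used (0 or 1".
- **Table.** The instruction is to "calculate the category score as the maximum of the category questions". A Yes on aids raises a score below 2 to 2. For No, the table says: "If the Aids/Devices indicator is 'No', no need to adjust the category score".
- **Missing-data text.** "If any of the category questions are missing, but the aids/device indicator is non-missing, the category score can still be computed". The only route to a missing category is the next sentence: "if all category questions and its aids/device indicators are missing, then the category score is considered missing".

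At the level of the total score, "If no more than 2 categories have missing category scores, then the HAQ-DI is the mean of the non-missing category scores", and "If more than 2 categories are missing, the HAQ-DI score is set to missing". Section 6.3.1.2 refers back to Appendix 1 for the algorithm and adds no rule for this case.

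**The concern.** Take a category in which the patient answers none of the functional questions but aids is recorded as No. The missing-data text does not make it missing, because the aids indicator is present. The formula then has one usable value, 0, the best possible score. The table has no question score to start from and nothing to leave unadjusted.

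Two programmers could therefore derive different HAQ-DI values from the same record, and one reading enters unanswered items as no disability. That reading also bypasses the rule that a total needs at least six scored categories.

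HAQ-DI change at Week 12 is a secondary endpoint (Section 6.3), and baseline HAQ-DI is a covariate in its model (Section 6.3.2). HAQ-DI is also one of the five items, of which three must improve, in ACR20/50/70 (Section 6.3.1.1).

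**Working it through.** **Inputs, all from Appendix 1:** eight categories; question scores 0 to 3; aids coded 0 or 1; at least six non-missing categories needed for a total.

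**Two scoring routes**

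- Route A (formula plus missing-data text): maximum of the non-missing values among the questions and 2 × aids; missing only if all of these are missing.
- Route B (table): maximum of the questions; unchanged if aids is No; raised to 2 if aids is Yes and the score is below 2.

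**Check on the plan's own example.** Dressing/grooming with both questions scored 1 and aids Yes: Route A gives max(1, 1, 2 × 1) = 2 and Route B gives 2. Both match the stated 2.

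| Functional questions | Aids | Route A | Route B |
|---|---|---|---|
| One answered 1, rest blank | No | max(1, 0) = 1 | 1 |
| All blank | Blank | missing | missing |
| All blank | No | 2 × 0 = 0, counted as non-missing | no score |
| All blank | Yes | 2 × 1 = 2 | no base score |

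The routes agree once at least one question is answered. The case at issue is the third row.

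**Effect on the total.** Let k be the number of such categories and m the mean of the other 8 − k.

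- Route A: (8 − k) × m / 8.
- Route B, with these categories treated as missing: m if k is 1 or 2; missing if k is 3 or more.
- Difference for k = 1 or 2: −k × m / 8, which is 12.5% or 25% of m.

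| Assumed m | k = 1: A vs B (difference) | k = 2: A vs B (difference) | k = 3: A vs B |
|---|---|---|---|
| 1.0 | 0.875 vs 1.0 (−0.125) | 0.75 vs 1.0 (−0.25) | 0.625 vs missing |
| 1.5 | 1.3125 vs 1.5 (−0.1875) | 1.125 vs 1.5 (−0.375) | 0.9375 vs missing |
| 2.0 | 1.75 vs 2.0 (−0.25) | 1.5 vs 2.0 (−0.50) | 1.25 vs missing |

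With all eight categories unanswered and aids No throughout, Route A reports 0 and Route B reports missing.

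**Effect on the ACR item under Route A**, assuming no true change and equal category scores:

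- Gap at Week 12 only: apparent improvement k/8, so 12.5% (k = 1) or 25% (k = 2). The second meets the 20% threshold. The 50% threshold needs k = 4 (50%), and the 70% threshold needs k = 6 (75%).
- Gap at baseline only: 1 − 8/(8 − k), so −14.3% (k = 1) or −33.3% (k = 2), an apparent worsening.
- Equal gaps at both visits: no apparent change.

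**The case against.** The strongest reply is that Appendix 1 never says outright that this case scores 0. The result needs the missing-data sentence to cover categories with every question blank, not just some, and it needs the maximum to ignore missing values. Other text leans towards missing. The Appendix 1 narrative lets the questions alone decide the score unless aids are required. Section 3.5.1 says missing data are generally not imputed unless a method is specified, and the observed-case rule in Section 6.1 leaves missing values missing.

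This does not remove the problem. If the sentence covers only partly answered categories, the all-blank case with aids No is covered by neither sentence and remains unfixed. The following sentence also favours the wider reading, since it requires the aids indicators to be missing too. A maximum that fails on a missing value would contradict the statement that a score is obtainable. The general rules give way to Appendix 1, which has its own missing-data rule.

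Three parts of the reply do stand:

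- The percentages compare two scoring rules; they do not measure error against the truth. A patient who truly had no difficulty in the blank category would be scored correctly by 0.
- The pattern may be rare. The SAP gives no frequency and does not say how unticked aids boxes are stored.
- The HAQ-DI item changes an ACR response only when it is the deciding item, on top of both joint-count criteria. The ACR50 and ACR70 figures need half or more of the categories blank.

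**Conclusion.** The concern holds. As written, the formula and missing-data text lead to a score of 0 for a category with no functional answer and aids No, and count it towards the six-category minimum. The table gives that category no score. The aids indicator serves elsewhere in the appendix only to raise a low score to 2, so a No carries no information about difficulty and should not create a score.

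Relative to the SAP's own mean over non-missing categories, HAQ-DI falls by 12.5% for one such category and 25% for two. From three on, a value appears where the table reading gives missing. Change from baseline moves towards improvement if the gap is after baseline and towards worsening if it is at baseline.

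The size in points depends on the assumed category mean, and the 0 depends on a maximum taken over non-missing values. A bias between arms would need gaps that differ by arm, which the SAP gives no reason to expect. The primary endpoint, DAS28(CRP), does not use HAQ-DI. This should be corrected, but it does not threaten the main conclusion of the trial.

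**What to change.** In Appendix 1, state that a category score is missing when none of its functional questions is answered and the aids indicator is No or missing. Say that the indicator acts only when it is Yes, where it sets a minimum of 2. A category with no functional answer and aids Yes therefore keeps the 2 that the formula already gives. Apply the six-category minimum after this step, and bring the formula, the table and the missing-data text into line.

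The cost is one sentence in the appendix and one line of code, and a few HAQ-DI scores may become missing. The choice should be fixed before treatment assignments are known to those who derive the score. If the SAP is already final, Section 1 requires the change to be documented in the clinical study report.

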**Appendix 2. RA Medication List**

WHO-DDE PREFERRED TERM	Biologic	Hydroxychloroquine	Methotrexate
ABATACEPT	y		
ADALIMUMAB	y		
ANAKINRA	y		
BIMEKIZUMAB	y		
CERTOLIZUMAB	y		
CERTOLIZUMAB PEGOL	y		
ETANERCEPT	y		
GOLIMUMAB	y		
HYDROXYCHLOROQUINE		y	
HYDROXYCHLOROQUINE SULFATE		y	
IMMUNOSUPPRESSANTS	y		
INFliximab	y		
METHOTREXATE			y
METHOTREXATE SODIUM			y
MONOCLONAL ANTIBODIES	y		
NORFLOX-TZ	y		
SARILUMAB	y		
SIRUKUMAB	y		
SULFASALAZINE			
TOCILIZUMAB	y		
TUMOR NECROSIS FACTOR ALPHA	y		
INVESTIGATIONAL DRUG (note: reported term is METHOTREXATE/PLACEBO )			y

### **Appendix 3.           Corticosteroid Medications**

Corticosteroid medications were searched in all the concomitant medication database using WHO ATC drug class Level 2 term “CORTICOSTEROIDS FOR SYSTEMIC USE”.
